2 OBJECTIVES AND ENDPOINTS

Objectives	Endpoints	Justification for Endpoints
Primary		
Demonstrate that same-session MRI-only simulation and treatment with stereotactic MRI-guided radiotherapy (SMART) for spinal oligometastases is feasible by confirming that the first fraction of same-session MRI-only simulation and treatment with SMART can be delivered on the first on-table attempt for at least 70% of patients.	Delivery of the first fraction of same-session MRI-only simulation and treatment with SMART within the first on-table attempt for at least 70% of patients.	Clinically relevant
Exploratory		
1. Determine the average time (days) from patient consult appointment to successful delivery of the first treatment fraction.	Average time (days) from patient consult appointment to successful delivery of the first treatment fraction.	Clinically relevant
2. Determine the local, in-field tumor response and control rates at three months.	Local control rate Local in-field tumor response	Clinically relevant
3. Demonstrate that same-session MR-only simulation and treatment with SMART for treatment of spinal metastases will lead to comparable toxicities compared with historically reported rates using standard, CT-based SBRT assessed prospectively at three months post-treatment and retrospectively for later time-points.	CTCAE version 5, treatment related Grade 3 or higher toxicities	Clinically relevant
4. Determine the projected dosimetric differences between the study method of MRI-only planning using standard	Dosimetric differences between MRI-only planning using standard bulk density	Generation of preliminary data for

bulk density override dose calculations (which will be clinically used for all patients) and an exploratory alternative method of a novel voxel-by-voxel MRI-based dose calculation using an institutionally developed machine learning algorithm (which will be simulated for comparison but not used in clinical treatment planning).
	
override dose calculations and voxel-by-voxel MRI-based dose calculation using MLA
	
future radiation planning techniques.

5. Determine the on-table time required for same-session MR-only simulation and treatment with plan generation for the initial treatment fraction and for subsequent treatment fractions.
	
On-table time required for initial treatment fraction and subsequent treatment fractions
	
Clinically relevant

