7 REGULATORY AND REPORTING REQUIREMENTS

The entities providing oversight of safety and compliance with the protocol require reporting as outlined below. Please refer to Appendix B for definitions and Appendix C for a grid of reporting timelines.

Adverse events will be tracked from start of treatment through the 3-month post-treatment follow-up visit. All adverse events must be recorded on the toxicity tracking case report form (CRF) with the exception of:

- Baseline adverse events, which shall be recorded on the medical history CRF
- Grade 1-2 AEs regardless of relatedness
- Grade 3-4 AEs that predate SBRT
- Grade 3-4 AEs that are not at least probably attributable to treatment

Refer to the data submission schedule in Section 9 for instructions on the collection of AEs in the EDC.

Reporting requirements for Washington University study team may be found in Section 7.1.

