7.2 Exceptions to Expedited Reporting

Events that do not require expedited reporting as described in Section 1.1 include:

- planned hospitalizations
- hospitalizations < 24 hours
- respite care
- events related to disease progression

Events that do not require expedited reporting must still be captured in the EDC.

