9.1 Adverse Event Collection in the Case Report Forms

All adverse events that occur beginning with start of treatment (minus exceptions defined in Section 7.0) must be captured in the Toxicity Form. Baseline AEs should be captured on the Medical History Form.

Participant death due to disease progression should be reported on the Toxicity Form as grade 5 disease progression. If death is due to an AE (e.g. cardiac disorders: cardiac arrest), report as a grade 5 event under that AE. Participant death must also be recorded on the Death Form.

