12 STATISTICAL CONSIDERATIONS

12.1 Stopping Criteria

If at any point in trial enrollment, >2 out of the first 5 patients, or >4 out of the first 10 patients experience symptoms of G3 or greater toxicity that is probably or definitely attributable to and did not pre-date SBRT, the trial will be suspended. Symptoms that pre-dated SBRT will not be count towards stopping criteria (example: thoracic spine patients requiring oxygen prior to and after SBRT will not be scored as G3 toxicity, however a new O2 requirement after RT would count towards stopping criteria). If at any time a grade 5 toxicity (death) is observed that is probably or definitely attributable to treatment, accrual will be suspended and the event will be reviewed by the principal investigator. Since patients accruing to the trial have metastatic disease, it is anticipated that deaths unrelated to the trial may be observed. Death that is felt either due to disease progression or patient comorbidity will not be scored as grade 5 toxicity and will not result in trial suspension.

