APPENDIX D: Reporting Timelines

Event	HRPO	QASMC
Serious AND unexpected suspected adverse reaction		
Unexpected fatal or life-threatening suspected adverse reaction		
Unanticipated problem involving risk to participants or others	Report within 10 working days. If the event results in the death of a participant enrolled at WU/BJH/SLCH, report within 1 working day.	Report via email after IRB acknowledgment
Major deviation	Report within 10 working days. If the event results in the death of a participant enrolled at WU/BJH/SLCH, report within 1 working day.	
A series of minor deviations that are being reported as a continuing noncompliance	Report within 10 working days.	
Protocol exception	Approval must be obtained prior to implementing the change	
Clinically important increase in the rate of a serious suspected adverse reaction of that listed in the protocol or IB		
Complaints	If the complaint reveals an unanticipated problem involving risks to participants or others OR noncompliance, report within 10 working days. If the event results in the death of a participant enrolled at WU/BJH/SLCH, report within 1 working day. Otherwise, report at the time of continuing review.	
Breach of confidentiality	Within 10 working days.	
Incarceration	If withdrawing the participant poses a safety issue, report within 10 working days.	

Event	HRPO	QASMC
	If withdrawing the participant does not represent a safety issue and the patient will be withdrawn, report at continuing review.	

Event	HRPO	QASMC
Adverse event or SAE that does not require expedited reporting	If they do not meet the definition of an unanticipated problem involving risks to participants or others, report summary information at the time of continuing review	Adverse events will be reported in the toxicity table in the DSM report which is typically due every 6 months.
Minor deviation	Report summary information at the time of continuing review.	
Complaints	If the complaint reveals an unanticipated problem involving risks to participants or others OR noncompliance, report within 10 working days. If the event results in the death of a participant enrolled at WU/BJH/SLCH, report within 1 working day. Otherwise, report at the time of continuing review.	
Incarceration	If withdrawing the participant poses a safety issue, report within 10 working days. If withdrawing the participant does not represent a safety issue and the patient will be withdrawn, report at continuing review.	

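### Grade 3-4 events rated below probably attributable are kept off the Toxicity Form, while the toxicity endpoint states no attribution level, so the form cannot show a wider rate

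*Combined protocol and SAP*

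**What the plan says.** **Collection.** Section 7 requires all adverse events from the start of treatment to the 3-month visit to go on the toxicity form, with four exceptions: baseline events, grade 1-2 events, grade 3-4 events that predate SBRT, and "Grade 3-4 AEs that are not at least probably attributable to treatment". Section 9.1 carries these over: "All adverse events that occur beginning with start of treatment (minus exceptions defined in Section 7.0) must be captured in the Toxicity Form".

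**Endpoint.** In Section 2 the third exploratory endpoint is "CTCAE version 5, treatment related Grade 3 or higher toxicities". Its objective is to show that the study method "will lead to comparable toxicities compared with historically reported rates using standard, CT-based SBRT". The evaluability table in Section 5.3 labels the endpoint simply as grade 3 or higher toxicity, without the relatedness qualifier. Section 12.3 promises descriptive statistics at three months and names no attribution level.

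**Stopping rule.** Section 12.1 does name a level; it counts "G3 or greater toxicity that is probably or definitely attributable to and did not pre-date SBRT".

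**Other capture rules.** Section 7.2 ends: "Events that do not require expedited reporting must still be captured in the EDC". For events that need no expedited reporting, Appendix D says: "Adverse events will be reported in the toxicity table in the DSM report which is typically due every 6 months".

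**The concern.** The fourth exception filters on a judgement rather than on a fact such as grade or date. A grade 3-4 event rated only possibly related is not entered with that rating; it is not entered on the form at all. The documents provide for no independent review of attribution.

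This matters most for the events of greatest interest. Section 5.2 lists sensory change, weakness and neuropathic pain as neurologic toxicities of concern, and Section 1.2 describes loss of neurologic function as tumours progress. The two can look alike, so a rating of possible is plausible for exactly these events.

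The endpoint is exploratory and descriptive, but safety still carries weight in the plan. Section 1.5 names it as one of two short-term goals. Section 12.3 makes keeping the safety profile of standard spine SBRT part of the condition for calling the pilot sufficient. If the historical rates used for comparison count possibly related events, the study's rate would be built on a narrower definition, and the form would hold nothing with which to check the difference.

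**Working it through.** There is no design figure to reproduce: Section 12.2 sets 10 evaluable patients on clinical grounds, with no power calculation and no toxicity rate. The check is mainly a comparison of texts.

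**1. Where an attribution level is stated**

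| Place | Level |
|---|---|
| Section 7, fourth exception (applied by 9.1) | probable or higher, grade 3-4 |
| Section 12.1, stopping rule | probable or definite |
| Section 2, endpoint | treatment related, level not given |
| Section 5.3, evaluability | none |
| Section 12.3, analysis | none |
| Appendix C | cites outside definitions of relatedness, sets no cut-off for the endpoint |

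The probable level governs the form and the stopping rule. No passage ties it to the endpoint.

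**2. What the form can yield for grade 3-4 events**

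- Rate at the probable level or above: available.
- Rate at the possible level or above: not available.
- All-cause rate: not available.

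Grade 5 events fall outside the exception. Section 9.1 puts deaths from progression on the Toxicity Form as grade 5, so the form already accepts events not attributed to treatment, though not at grade 3-4. Section 12.1 separately keeps such deaths out of the toxicity count: "Death that is felt either due to disease progression or patient comorbidity will not be scored as grade 5 toxicity".

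**3. Whether another passage recovers the omitted events**

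Section 7.2 wants events that need no expedited reporting, including those related to progression, in the electronic database. It names no form. Section 7 points to Section 9 for database collection, and Section 9.1 returns to the Toxicity Form with the same exceptions. The Section 9 schedule lists no other form for adverse events during treatment. Appendix D sends such events to the monitoring report's toxicity table with no attribution limit. These passages conflict with Sections 7 and 9.1 and do not say where an excluded event is held.

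**4. Scale at n = 10**

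Inputs: n = 10 (Section 12.2), assuming all 10 evaluable patients receive study treatment, as Section 5.3 requires for the toxicity endpoint. The numbers of omitted patients are illustrative.

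One patient changes the rate by 1/10 = 10 percentage points.

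Exact (Clopper-Pearson) 95% limits for x of n: the lower limit is the 2.5% quantile of Beta(x, n - x + 1), taken as 0 when x = 0. The upper limit is the 97.5% quantile of Beta(x + 1, n - x).

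| Patients with an event | Rate | Exact 95% interval |
|---|---|---|
| 0/10 | 0% | 0% to 30.8% |
| 1/10 | 10% | 0.3% to 44.5% |
| 2/10 | 20% | 2.5% to 55.6% |

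If the form shows 0/10 and one patient was omitted, the upper limit that should have been reported is 44.5%, not 30.8%. With two omitted it is 55.6%.

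The chance that at least one of 10 patients has an omitted event is 1 - (1 - p)^10, where p is the assumed chance per patient. For p = 5%, 10%, 20% and 30% it is 40%, 65%, 89% and 97%. The documents give no value for p.

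**The case against.** The strongest reply is that nothing the plan promises is lost. The endpoint is limited to treatment-related events, and the only two passages that set a level use probable or higher. The natural reading is that the endpoint does too, and on that reading its rate is unaffected. The wider rates are promised nowhere. Light collection also looks deliberate: Section 12.3 calls spine SBRT standard of care and says further prospective toxicity assessment is not needed. Objective 3 allows retrospective assessment, and a chart review of 10 patients at one centre is feasible. Section 5.2 describes skin and thoracic toxicity assessment without an attribution filter. The historical comparison also lacks a comparator rate or margin, so it could not be settled even with full recording. One phrase in Section 2 would close the ambiguity.

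Much of this stands. The endpoint is exploratory, the probable level may well be what was meant, the interval shifts are what one event does in any sample of 10, and recording more events does not supply the missing comparator.

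It does not remove the point. The retrospective clause covers only time-points after three months. The remark in Section 12.3 argues against further assessment, while the same section makes the safety profile part of the success condition. The unfiltered assessments in Section 5.2 add to the inconsistency over what is recorded. Stating the level in Section 2 would define the endpoint, but it would still leave the attribution judgement unrecorded for every event that it excludes.

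**Conclusion.** The concern holds as a design choice that should be changed. The Toxicity Form excludes grade 3-4 events rated below probable, the endpoint gives no attribution level, and so the form cannot show an at-least-possible or all-cause grade 3-4 rate.

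Whether this biases the reported rate is conditional. It does so only if the intended or historical definition includes possibly related events, or if events caused by treatment are rated below probable. The documents settle neither, so the size is unknown. No decision threshold is tied to the toxicity rate.

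Not affected: the primary feasibility endpoint, the stopping count in Section 12.1, events rated probable or definite, and the recording of grade 5 events. Confidence is medium, because the omitted events might be held somewhere in the database that the documents do not name.

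**What to change.** 1. In Section 7, delete the fourth exception and keep the other three. Every grade 3-5 event from the start of treatment to the 3-month visit that did not predate SBRT then goes on the Toxicity Form with its grade and attribution category.
2. In Section 2, state the attribution level that defines the endpoint for objective 3.
3. In Section 12.3, report the rate at that level as the endpoint, with the all-cause grade 3 or higher rate beside it as a descriptive check.
4. Reconcile Sections 7 and 9.1 with Section 7.2 and with the Appendix D row on events that need no expedited reporting, and name the form that holds those events.
5. Leave Section 12.1 as it is.

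The cost should be small: additional form entries for about 10 patients with one follow-up visit, although the documents give no event rate from which to count them. The all-cause rate will include events caused by the tumour or by other illness and may look less favourable. That is why it is shown beside the defined endpoint and does not replace it.

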7.1 WU PI Reporting Requirements

7.1.1 Reporting to the Human Research Protection Office (HRPO) at Washington University

Reporting will be conducted in accordance with Washington University IRB Policies.

Pre-approval of all protocol exceptions must be obtained prior to implementing the change.

7.1.2 Reporting to the Quality Assurance and Safety Monitoring Committee (QASMC) at Washington University

The PI (or designee) is required to notify the QASMC of any unanticipated problems involving risks to participants or others occurring at WU or any BJH or SLCH institution that has been reported to and acknowledged by HRPO. (Unanticipated problems reported to HRPO and withdrawn during the review process need not be reported to QASMC.)

QASMC must be notified within **10 days** of receipt of IRB acknowledgment via email to [contact]. Submission to QASMC must include the myIRB form and any supporting documentation sent with the form.

7.2 Exceptions to Expedited Reporting

Events that do not require expedited reporting as described in Section 1.1 include:

- planned hospitalizations
- hospitalizations < 24 hours
- respite care
- events related to disease progression

Events that do not require expedited reporting must still be captured in the EDC.

8 STUDY CALENDAR

	Screening	Pre-Treatment	D1	D2	D3	D4	D5	3 mos post-SBRT ¹
Informed consent	X							
Medical history	X							
Volumetric imaging	X ⁵							X
Pregnancy test ²	X							
Adaptive SBRT			X	X	X ³	X ³	X ³	
Adverse events assessment		X	X -----X					

1. Window is 10-14 weeks post-completion of SBRT

2. Women of childbearing potential only; within 14 days of start of treatment

3. Treatment days 3,4,5 are for a 5-fraction course of treatment only. If a 2-fraction course is selected, then there would be only two treatment days.

5. Collection of a standard of care diagnostic CT scan completed in the past 6 months

9 DATA SUBMISSION SCHEDULE

Case report forms with appropriate source documentation will be completed according to the schedule listed in this section.

Case Report Form	Submission Schedule
Original Consent Form	Prior to registration
On-Study Form	Prior to starting treatment
Treatment Summary Form	End of treatment
Toxicity Form	During treatment and at 3-mo f/u
Follow Up Form	3-mo f/u

9.1 Adverse Event Collection in the Case Report Forms

All adverse events that occur beginning with start of treatment (minus exceptions defined in Section 7.0) must be captured in the Toxicity Form. Baseline AEs should be captured on the Medical History Form.

Participant death due to disease progression should be reported on the Toxicity Form as grade 5 disease progression. If death is due to an AE (e.g. cardiac disorders: cardiac arrest), report as a grade 5 event under that AE. Participant death must also be recorded on the Death Form.

10 MEASUREMENT OF EFFECT

10.1 Antitumor Effect – Solid Tumors

For the purposes of this study, patients should be re-evaluated for response at the 3-month follow-up visit.

Response and progression will be evaluated in this study using the new international criteria proposed by the revised Response Evaluation Criteria in Solid Tumors (RECIST) guideline (version 1.1) [Eur J Ca 45:228-247, 2009]. Changes in the largest diameter (unidimensional measurement) of the tumor lesions and the shortest diameter in the case of malignant lymph nodes are used in the RECIST criteria.

10.2 Disease Parameters

Measurable disease: Measurable lesions are defined as those that can be accurately measured in at least one dimension (longest diameter to be recorded) as >20 mm by chest x-ray, as >10 mm with CT scan, or >10 mm with calipers by clinical exam. All tumor measurements must be recorded in millimeters (or decimal fractions of centimeters).

Malignant lymph nodes: To be considered pathologically enlarged and measurable, a lymph node must be >15 mm in short axis when assessed by CT scan (CT scan slice thickness recommended to be no greater than 5 mm). At baseline and in follow-up, only the short axis will be measured and followed.

Non-measurable disease: All other lesions (or sites of disease), including small lesions (longest diameter <10 mm or pathological lymph nodes with ≥ 10 to <15 mm short axis), are considered non-measurable disease. Bone lesions, leptomeningeal disease, ascites, pleural/pericardial effusions, lymphangitis cutis/pulmonitis, inflammatory breast disease, and abdominal masses (not followed by CT or MRI), are considered as non-measurable.

Note: Cystic lesions that meet the criteria for radiographically defined simple cysts should not be considered as malignant lesions (neither measurable nor non-measurable) since they are, by definition, simple cysts.

‘Cystic lesions’ thought to represent cystic metastases can be considered as measurable lesions, if they meet the definition of measurability described above. However, if non-cystic lesions are present in the same patient, these are preferred for selection as target lesions.

Target lesions: All measurable lesions up to a maximum of 2 lesions per organ and 5 lesions in total, representative of all involved organs, should be identified as target lesions and recorded and measured at baseline. Target lesions should be selected on the basis of their size (lesions with the longest diameter), be representative of all involved organs, but in addition should be those that lend themselves to reproducible repeated measurements. It may be the case that, on occasion, the largest lesion does not lend itself to reproducible measurement in which circumstance the next largest lesion which can be measured reproducibly should be selected. A sum of the diameters (longest for non-nodal lesions, short axis for nodal lesions) for all target lesions will be calculated and reported as the baseline sum diameters. If lymph nodes are to be included in the sum, then only the short axis is added into the sum. The baseline sum diameters will be used as reference to further characterize any objective tumor regression in the measurable dimension of the disease.

Non-target lesions: All other lesions (or sites of disease) including any measurable lesions over and above the 5 target lesions should be identified as non-target lesions and should also be recorded at baseline. Measurements of these lesions are not required, but the presence, absence, or in rare cases unequivocal progression of each should be noted throughout follow-up.

10.3 Methods for Evaluation of Measurable Disease

All measurements should be taken and recorded in metric notation using a ruler or calipers. All baseline evaluations should be performed as closely as possible to the beginning of treatment and never more than 4 weeks before the beginning of the treatment.

The same method of assessment and the same technique should be used to characterize each identified and reported lesion at baseline and during follow-up. Imaging-based evaluation is preferred to evaluation by clinical examination unless the lesion(s) being followed cannot be imaged but are assessable by clinical exam.

Clinical lesions: Clinical lesions will only be considered measurable when they are superficial (e.g., skin nodules and palpable lymph nodes) and ≥ 10 mm diameter as assessed using calipers (e.g., skin nodules). In the case of skin lesions, documentation by color photography, including a ruler to estimate the size of the lesion, is recommended.

Chest x-ray: Lesions on chest x-ray are acceptable as measurable lesions when they are clearly defined and surrounded by aerated lung. However, CT is preferable.

Conventional CT and MRI: This guideline has defined measurability of lesions on CT scan based on the assumption that CT slice thickness is 5 mm or less. If CT scans have slice thickness greater than 5 mm, the minimum size for a measurable lesion should be twice the slice thickness. MRI is also acceptable in certain situations (e.g. for body scans).

Use of MRI remains a complex issue. MRI has excellent contrast, spatial, and temporal resolution; however, there are many image acquisition variables involved in MRI, which greatly impact image quality, lesion conspicuity, and measurement. Furthermore, the availability of MRI is variable globally. As with CT, if an MRI is performed, the technical specifications of the scanning sequences used should be optimized for the evaluation of the type and site of disease. Furthermore, as with CT, the modality used at follow-up should be the same as was used at baseline and the lesions should be measured/assessed on the same pulse sequence. It is beyond the scope of the RECIST guidelines to prescribe specific MRI pulse sequence parameters for all scanners, body parts, and diseases. Ideally, the same type of scanner should be used and the image acquisition protocol should be followed as closely as possible to prior scans. Body scans should be performed with breath-hold scanning techniques, if possible.

PET-CT: At present, the low dose or attenuation correction CT portion of a combined PET-CT is not always of optimal diagnostic CT quality for use with RECIST measurements. However, if the site can document that the CT performed as part of a PET-CT is of identical diagnostic quality to a diagnostic CT (with IV and oral contrast), then the CT portion of the PET-CT can be used for RECIST measurements and can be used interchangeably with conventional CT in accurately measuring cancer lesions over time. Note, however, that the PET portion of the CT introduces additional data which may bias an investigator if it is not routinely or serially performed.

Ultrasound: Ultrasound is not useful in assessment of lesion size and should not be used as a method of measurement. Ultrasound examinations cannot be reproduced in their entirety for independent review at a later date and, because they are operator dependent, it cannot be guaranteed that the same technique and measurements will be taken from one assessment to the next. If new lesions are identified by ultrasound in the course of the

study, confirmation by CT or MRI is advised. If there is concern about radiation exposure at CT, MRI may be used instead of CT in selected instances.

Endoscopy, Laparoscopy: The utilization of these techniques for objective tumor evaluation is not advised. However, such techniques may be useful to confirm complete pathological response when biopsies are obtained or to determine relapse in trials where recurrence following complete response (CR) or surgical resection is an endpoint.

Tumor markers: Tumor markers alone cannot be used to assess response. If markers are initially above the upper normal limit, they must normalize for a patient to be considered in complete clinical response. Specific guidelines for both CA-125 response (in recurrent ovarian cancer) and PSA response (in recurrent prostate cancer) have been published [JNCI 96:487-488, 2004; J Clin Oncol 17, 3461-3467, 1999; J Clin Oncol 26:1148-1159, 2008]. In addition, the Gynecologic Cancer Intergroup has developed CA-125 progression criteria which are to be integrated with objective tumor assessment for use in first-line trials in ovarian cancer [JNCI 92:1534-1535, 2000].

Cytology, Histology: These techniques can be used to differentiate between partial responses (PR) and complete responses (CR) in rare cases (e.g., residual lesions in tumor types, such as germ cell tumors, where known residual benign tumors can remain).

The cytological confirmation of the neoplastic origin of any effusion that appears or worsens during treatment when the measurable tumor has met criteria for response or stable disease is mandatory to differentiate between response or stable disease (an effusion may be a side effect of the treatment) and progressive disease.

FDG-PET: While FDG-PET response assessments need additional study, it is sometimes reasonable to incorporate the use of FDG-PET scanning to complement CT scanning in assessment of progression (particularly possible 'new' disease). New lesions on the basis of FDG-PET imaging can be identified according to the following algorithm:

- Negative FDG-PET at baseline, with a positive FDG-PET at follow-up is a sign of PD based on a new lesion.
- No FDG-PET at baseline and a positive FDG-PET at follow-up: If the positive FDG-PET at follow-up corresponds to a new site of disease confirmed by CT, this is PD. If the positive FDG-PET at follow-up is not confirmed as a new site of disease on CT, additional follow-up CT scans are needed to determine if there is truly progression occurring at that site (if so, the date of PD will be the date of the initial abnormal FDG-PET scan). If the positive FDG-PET at follow-up corresponds to a pre-existing site of disease on CT that is not progressing on the basis of the anatomic images, this is not PD.
- FDG-PET may be used to upgrade a response to a CR in a manner similar to a biopsy in cases where a residual radiographic abnormality is thought to represent fibrosis or scarring. The use of FDG-PET in this circumstance should be prospectively described in the protocol and supported by disease-specific medical literature for the indication. However, it must be acknowledged that both

approaches may lead to false positive CR due to limitations of FDG-PET and biopsy resolution/sensitivity.

Note: A 'positive' FDG-PET scan lesion means one which is FDG avid with an uptake greater than twice that of the surrounding tissue on the attenuation corrected image.

